5.1.2 Planned number of subjects and sites

It is estimated that approximately 650 to 720 subjects from N01358 will enter the study, based on the assumption that at least 90% of randomized subjects from N01358 will complete N01358 and enroll in N01379. Up to 100 subjects from N01258 may also be eligible for enrollment.

It is estimated that 120 sites from N01358 and up to 25 sites from N01258 will participate in the study.

5.1.3 Anticipated regions and countries

The regions and countries for enrollment will be the same as in the previous studies, N01358 and N01258. N01358 is planned to be performed in North America (Canada and USA), Western Europe, Latin America, Eastern Europe, Asia, and Africa, and N01258 is planned to be performed in the USA and Europe, with possible extension to other countries or regions for both studies.

5.2 Schedule of study assessments

Table 5-1: Schedule of study assessments

	Entry Visit (EV)	Full Evaluation Visit (FEV)	Minimal Evaluation Visit (MEV)	Yearly Evaluation Visit (YEV)	Last Evaluation Period Visit (or Early Discontinuation Visit [EDY]/D)	Down-Titration Phone Call (DTP) ^a	Final Visit (FV)	Reference to Section
Visit	V1	V3, V5, V9...	V2, V4, V6, V8, V10...	V7...	NA	NA	NA	5.3
Month	M0	M2, M6, M18...	M1, M3, M9, M15, M21...	M12...	NA	NA	NA	5.3
ASSESSMENTS								
Written Informed Consent	X							13.1
Written Informed Consent for DNA analysis (for subjects from N01358)	X							13.1
Subject identification card dispensing	X							13.2
Verification inclusion/ exclusion criteria	X							6
Demographic data	X							8.1
Childbearing potential	X							8.1
General medical and procedures history	X ^b							8.1
Epilepsy history	X ^b							8.1
AED history	X ^b							8.1
Vital signs	X ^c	X	X	X	X		X	10.6.2

Table 5-1: Schedule of study assessments

	Entry Visit (EV)	Full Evaluation Visit (FEV)	Minimal Evaluation Visit (MEV)	Yearly Evaluation Visit (YEV)	Last Evaluation Period Visit (or Early Discontinuation Visit [EDV])	Down-Titration Phone Call (DTP) ^a	Final Visit (FV)	Reference to Section
Visit	V1	V3, V5, V9...	V2, V4, V6, V8, V10...	V7...	NA	NA	NA	5.3
Month	M0	M2, M6, M18...	M1, M3, M9, M15, M21...	M12...	NA	NA	NA	5.3
Weight and height ^d	X	X		X	X		X	10.6.3
Physical examination	X ^c	X		X	X		X	10.6.4
Neurological examination	X ^c	X		X	X		X	10.6.5
ECG ^e	X ^c	X		X	X		X	10.6.1
IVRS call	X	X	X	X	X		X	7.10
Daily record card dispensed	X	X	X	X	X			9
Daily record card retrieved		X	X	X	X		X	9
Recording of seizures	X ^b	X	X	X	X		X	9
QOLIE-31-P ^f		X		X	X			9.1.1
HADS ^f		X		X	X			10.6.7
Socio-professional data ^g				X	X			9.1.2
Hospital stays ^g	X ^c	X	X	X	X			9.1.5
Healthcare provider consultations not foreseen by protocol ^g	X ^c	X	X	X	X			9.1.4
Laboratory safety assessments ^h	X ^c	X	X ⁱ	X	X		X	10.5.1

This document cannot be used to support any marketing application and any extensions thereof. REDACTED COPY - marketing authorization application and any extensions thereof.

Table 5-1: Schedule of study assessments

	Entry Visit (EV)	Full Evaluation Visit (FEV)	Minimal Evaluation Visit (MEV)	Yearly Evaluation Visit (YEV)	Last Evaluation Period Visit (or Early Discontinuation Visit [EDV])	Down-Titration Phone Call (DTP) ^a	Final Visit (FV)	Reference to Section
Visit	V1	V3, V5, V9...	V2, V4, V6, V8, V10...	V7...	NA	NA	NA	5.3
Month	M0	M2, M6, M18...	M1, M3, M9, M15, M21...	M12...	NA	NA	NA	5.3
Blood sampling for the DNA analysis ^l	X							10.5.2
Recording of AEs	X ^k	X	X	X	X	X	X	10.1
C-SSRS	X	X	X	X	X	X	X	10.6.6
Medical procedures	X	X	X	X	X	X	X	9.1.3
Concomitant AED	X ^l	X	X	X	X	X	X	7.8
Concomitant non-AED	X ^l	X	X	X	X	X	X	7.8
Drug dispensing	X	X	X	X	X	X	X	7
Drug return/accountability		X	X	X	X	X	X	7
End of study status ^m					X		X	8.8

AE=adverse event; AED=antiepileptic drug; CRF=Case Report Form; C-SSRS=Columbia-Suicide Severity Rating Scale; DNA=deoxyribonucleic acid; DTP=Down-Titration Phone Call; ECG=electrocardiogram; EDV=Early Discontinuation Visit; EV=Entry Visit; FEV=Full Evaluation Visit; FV=Final Visit; HADS=Hospital Anxiety and Depression Scale; IVRS=interactive voice response system; M=Month; MEV=Minimal Evaluation Visit; NA=not applicable; QOLIE-31-P=Patient Weighted Quality of Life in Epilepsy Inventory; V=Visit; YEV=Y early Evaluation Visit
 Note: Months and visit numbers are displayed for the first 2 years. The visit schedule described in Section 5.3 will be applied.
 Note: At the EV, the IVRS call will be part of the N01358 or N01258 final visit.
^a The Down-Titration Phone Call at the end of the Down-Titration Period is mandatory.
^b General medical and procedures history, AED history, recording of seizures, and epilepsy history will be obtained from the Baseline of N01358 or N01258 and do not need to be recorded on the CRF for this study.

Table 5-1: Schedule of study assessments

	Entry Visit (EV)	Full Evaluation Visit (FEV)	Minimal Evaluation Visit (MEV)	Yearly Evaluation Visit (YEV)	Last Evaluation Period Visit (or Early Discontinuation Visit [EDV])	Down-Titration Phone Call (DTP) ^a	Final Visit (FV)	Reference to Section
Visit	V1	V3, V5, V9...	V2, V4, V6, V8, V10...	V7...	NA	NA	NA	5.3
Month	M0	M2, M6, M18...	M1, M3, M9, M15, M21...	M12...	NA	NA	NA	5.3

^c The following will be obtained from the last visit of N01358 or N01258 and do not need to be recorded on the CRF for this study: physical and neurological examination, vital signs, hospital stays, healthcare provider consultations not foreseen by the protocol, ECG, and laboratory assessments (hematology, blood chemistry, and urinalysis).

^d Height will be obtained at Visit 1 in N01358 or N01258.

^e At the FV, an ECG is mandatory, except if the FV follows an EDV where ECG results were normal.

^f QOLIE-31-P and HADS are to be completed at the beginning of the visit by all subjects who are able to complete the assessments on their own. These will be collected only for the first 2 years.

^g Socio-professional data, hospital stays, and healthcare provider consultations not foreseen by the protocol will be collected for all subjects for the first 2 years.

^h Laboratory safety assessment includes hematology, blood chemistry, and urinalysis; where applicable (women with childbearing potential), a urine pregnancy test will be done. Endocrinology will be assessed at each YEV. In addition, liver function tests as described in Section 10.5.1 will be performed at the MEV in M3 and M9. Laboratory assessment is mandatory at the FV, except if the FV follows an EDV where laboratory results were normal. The result of the calculated creatinine clearance will be provided by the central laboratory.

ⁱ Liver function tests are the only laboratory assessments done at the MEV in M3 and M9 (see Section 10.5.1).

^j The DNA analysis is part of N01379 and will be performed only in adult subjects from N01358 after signing an additional Informed Consent form and where ethically accepted and authorized by regulatory agencies. Mentally impaired subjects will be excluded from the DNA analysis.

^k Ongoing AEs at the time of subject completion of N01358 or N01258 will be obtained from the database for N01358 or N01258 and should not be recorded on the CRF for N01379 unless there is a change in intensity or seriousness. In this event, the AE should be recorded on the CRF for N01379 with the onset date corresponding to the date of change in condition.

^l Ongoing medications (AEDs and non-AEDs) at the time of subject completion of N01358 or N01258 will be obtained from the database for N01358 or N01258 and should not be recorded on the CRF for N01379 unless there is a change regarding the administration of the medication. In this event, the medication should be recorded on the CRF for N01379 with the start date corresponding to the date of change in administration.

^m End of study status will be completed at the FV for subjects having performed an EDV and down-titration of BRV (discontinued subjects) and for subjects

Table 5-1: Schedule of study assessments

	Entry Visit (EV)	Full Evaluation Visit (FEV)	Minimal Evaluation Visit (MEV)	Yearly Evaluation Visit (YEV)	Last Evaluation Period Visit (or Early Discontinuation Visit [EDV])	Down-Titration Phone Call (DTP) ^a	Final Visit (FV)	Reference to Section
Visit	V1	V3, V5, V9...	V2, V4, V6, V8, V10...	V7...	NA	NA	NA	5.3
Month	M0	M2, M6, M18...	M1, M3, M9, M15, M21...	M12...	NA	NA	NA	5.3

leaving the study at the end of the program (completed subjects). Alternatively, end of study status will be completed at the EDV for subjects who may transition into another BRV study, or be initiated without down-titration in a managed access program, named patient program, compassionate use program, or similar type of access program as allowed per country-specific legal and regulatory requirements, or for subjects who will be converted without down-titration to commercial BRV if, when, and where available.

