8.1 Entry Visit

- Written Informed Consent
- Additional written Informed Consent for subjects agreeing to DNA analysis
- Subject identification card dispensing
- Verification inclusion/exclusion criteria
- Demographic data
- Childbearing potential
- Weight
- IVRS call
- Daily record card (DRC) dispensed
- Medical procedures
- Blood sampling for the DNA analysis for consenting subjects coming from N01358. The DNA analysis will be performed in adult subjects where ethically accepted and authorized by regulatory agencies.
- Concomitant AED
- Concomitant non-AED

Ongoing medications (AEDs and non-AEDs) at the time of subject completion of N01358 or N01258 will be obtained from the database for N01358 or N01258 and should not be recorded on the CRF for N01379 unless there is a change regarding the administration of the medication. In this event, the medication should be recorded on the CRF for N01379 with the start date corresponding to the date of change in administration.

- Recording of AEs

Ongoing AEs at the time of subject completion of N01358 or N01258 will be obtained from the database for N01358 or N01258 and should not be recorded on the CRF for N01379 unless there is a change in intensity or seriousness. In this event, the AE should be recorded on the CRF for N01379 with the onset date corresponding to the date of change in condition.

- Drug dispensing
- Appointment for the next visit according to the schedule described in Section 5.3

The following data will be obtained from the Baseline of N01358 or N01258 and do not need to be recorded on the CRF for this study.

- General medical and procedures history
- AED history
- Recording of seizures
- Epilepsy history

The following data will be obtained from the last visit of N01358 or N01258 and do not need to be recorded on the CRF for this study.

- Vital signs
- Neurological examination
- Physical examination
- ECG
- Laboratory safety assessments: hematology, blood chemistry, urinalysis, and urine pregnancy test (if applicable)
- Hospital stays
- Suicidality assessment (C-SSRS)
- Healthcare provider consultations not foreseen by the protocol

Height will be obtained from Visit 1 in N01358 or N01258.

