10 ASSESSMENT OF SAFETY

10.1 Adverse events

10.1.1 Definition of adverse event

An AE is any untoward medical occurrence in a patient or clinical investigation subject administered a pharmaceutical product which does not necessarily have a causal relationship with this treatment. An AE can therefore be any unfavorable and unintended sign (including an abnormal laboratory finding), symptom, or disease temporally associated with the use of a medicinal (investigational) product, whether or not related to the medicinal (investigational) product.

In order to ensure complete safety data collection, all AEs occurring during the study (ie, after signing the Informed Consent form), including any pretreatment and posttreatment periods required by the protocol, must be reported in the CRF even if no investigational product was taken but specific study procedures were conducted. This includes all AEs not present prior to the initial visit and all AEs which recurred or worsened after the initial visit.

Signs or symptoms of the condition/disease for which the investigational product is being studied should be recorded as AEs only if their nature changes considerably or their frequency or intensity increases in a clinically significant manner as compared to the clinical profile known to the Investigator from the subject's history or the Baseline Period.

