10.1.3 Description of adverse events

When recording an AE, the Investigator should use the overall diagnosis or syndrome using standard medical terminology, rather than recording individual symptoms or signs. The CRF and source documents should be consistent. Any discrepancies between the subject's own words on his/her own records (eg, diary card) and the corresponding medical terminology should be clarified in the source documentation.

Details for completion of the Adverse Event CRF (including judgment of relationship to study medication) are described in the CRF Completion Guidelines.

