10.1.5 Rule for repetition of an adverse event

An increase in the intensity of an AE should lead to the repetition of the AE being reported with:

- The outcome date of the first AE that is not related to the natural course of the disease being the same as the start date of the repeated AE, and the outcome of “worsening”
- The AE verbatim term being the same for the first and repeated AE, so that the repeated AE can be easily identified as the worsening of the first one

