3.2 Analysis time points

3.2.1 First and last dose of BRV

Unless otherwise noted, all references to the first dose of BRV in this SAP refer to the first dose of BRV during N01379 (ie, not the first dose of BRV from the previous study in which subjects participated in prior to N01379). Unless otherwise noted, all references to the last known dose of BRV in this SAP refer to the last dose of BRV taken across any study periods (ie, not necessarily the last dose of BRV during the Evaluation Period).

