11.2 Adverse events

11.2.1 Definition of treatment-emergent AE

AEs will be classified as either pre-study or treatment-emergent. Pre-study AEs are defined as AEs which had onset prior to the date of the first dose of BRV. TEAEs are defined as AEs that had onset on or after the day of first BRV dose. AEs with an incomplete onset date will be classified as TEAEs if the month and year of onset (when only the month and year are specified) is the same as the month and year of the first BRV dose or the year of onset (when only year is specified) is the same as the year of first BRV dose.

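### The rule for adverse events carried over from N01358/N01258 does not say that a change must be a worsening, and the SAP's date-only TEAE definition would count an improvement entered under it as a TEAE

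*Protocol*

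**What the plan says.** **Carry-over rule.** Protocol Table 5-1, footnote k, and Section 8.1 take events ongoing at the end of N01358 or N01258 from the core-study database. Such an event "should not be recorded on the CRF for N01379 unless there is a change in intensity or seriousness". When that condition is met, "the AE should be recorded on the CRF for N01379 with the onset date corresponding to the date of change in condition".

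**General reporting rules.** Protocol 10.1.1 describes what must be reported: "This includes all AEs not present prior to the initial visit and all AEs which recurred or worsened after the initial visit". Protocol 10.1.5 covers repeat records: "An increase in the intensity of an AE should lead to the repetition of the AE being reported with" an outcome of worsening for the first record and the same verbatim term for both. Protocol 10.1.3 defers further detail: "Details for completion of the Adverse Event CRF (including judgment of relationship to study medication) are described in the CRF Completion Guidelines". Those guidelines are not among the documents.

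**Analysis rule.** SAP 11.2.1 states: "TEAEs are defined as AEs that had onset on or after the day of first BRV dose". SAP 3.2.1 fixes the reference point: "all references to the first dose of BRV in this SAP refer to the first dose of BRV during N01379". Protocol 7.2 places the first intake on the evening of the Entry Visit day.

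**Role.** Occurrence of a TEAE is a primary safety variable (Protocol 4.1.1; SAP 2.2.1.1).

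**The concern.** The trigger in footnote k and 8.1 is a change without a direction. An event that goes from severe to mild has changed in intensity, so on the plain words it gets a new N01379 record with a new onset date. SAP 11.2.1 looks only at that date. It does not compare the record with the last core-study intensity and does not set improvements aside, so a subject who is getting better could be tabulated as having a new on-treatment event.

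Such records would enter the SAP 11.2.2 outputs: the total number of TEAEs, incidence by preferred term, the 3-month interval tables, the tables restricted to terms seen in at least 5% of subjects, and the split by randomized treatment in the previous study. Improvement soon after entry is plausible. N01358 had a 200mg/day arm, all its subjects start N01379 at 150mg/day, and later dose changes may respond to tolerability. The documents do not say how often it happens.

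**Working it through.** The plan states no figure on this point, so there is nothing to reproduce. The check applies the rules in order and then gives an illustrative size.

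**Step 1: apply the rules.** Day 1 is the day of first dose in N01379. An event is a TEAE if its onset day is Day 1 or later. Under footnote k and 8.1 the onset is the day of change.

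| Carried-over event | Entered under literal footnote k / 8.1? | TEAE under SAP 11.2.1? | TEAE if entry is limited to worsening? |
|---|---|---|---|
| Unchanged | No | No | No |
| Worsens on Day 30 | Yes | Yes | Yes |
| Improves on Day 30 | Yes | Yes | No |
| Improves on the Entry Visit day, first dose that evening | Yes | Yes | No |

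The two readings differ only for improvements: one TEAE record under the literal wording, none under a worsening-only rule.

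**Step 2: illustrative size.**

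Inputs:
- N, entrants (Protocol 5.1.2): 650 to 720 from N01358 and up to 100 from N01258. The range is 650 + 0 = 650 to 720 + 100 = 820.
- f, the share of subjects whose only re-entered event is an improvement: assumed 2% to 10%.
- p, the share of those subjects who also have another TEAE: assumed 50% to 90%.

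Extra TEAE records, at one per affected subject, are N × f:
- low: 650 × 0.02 = 13
- high: 820 × 0.10 = 82

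The rise in the share of subjects with at least one TEAE is f × (1 − p):
- low: 0.02 × (1 − 0.90) = 0.002, or 0.2 percentage points (650 × 0.002 = 1.3 subjects)
- middle: 0.05 × (1 − 0.70) = 0.015, or 1.5 points
- high: 0.10 × (1 − 0.50) = 0.05, or 5.0 points (820 × 0.05 = 41 subjects)

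**Step 3: the 5% tables.** The cut-off is 0.05 × 650 = 32.5 to 0.05 × 820 = 41 subjects per term. A term just under that count could cross it on a few added subjects. Whether any term would do so cannot be judged from the documents.

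**The case against.** The strongest case on the other side is that the protocol, read as a whole, already means worsening. The adverse-event row of Table 5-1 refers to Section 10.1, where 10.1.1 names recurrence and worsening and 10.1.5 ties a repeat record to increased intensity. Footnote k says should, never mentions improvement, and is attached to the Entry Visit cell only. The CRF Completion Guidelines may settle the matter. The study is single-arm and descriptive, so no test is affected, and any error over-reports events.

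Much of this stands. A reader might infer that the protocol orders sites to report improvements as new events, and that TEAE incidence is therefore inflated. The documents do not support that: the wording is undirected, not explicit, and what sites recorded is unknown. Nor is there a flat contradiction, because neither 10.1.1 nor 10.1.5 says that worsening is the only ground for a record.

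The objection does not remove the problem. Footnote k and 8.1 are the only rules specific to carried-over events, so a site would naturally turn to them. The paired records in 10.1.5 do not fit a carried-over event, because its first record sits in another study's database. Sections 10.1.1 and 10.1.5 do not exclude improvements. Whatever the guidelines say, SAP 11.2.1 as written has no filter if such records exist.

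**Conclusion.** The point holds as an inconsistency between footnote k / 8.1 and 10.1.1 / 10.1.5, with no safeguard in SAP 11.2.1. If sites followed the literal wording, improvements in carried-over events on or after the first-dose day would count as TEAEs.

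The size is not known. The range of 0.2 to 5.0 percentage points rests entirely on the assumed f and p, and its upper end needs 10% of subjects to be affected and half of those to have no other TEAE. Record counts and preferred-term incidences are more exposed than the subject-level primary variable, because another unrelated TEAE does not mask them.

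Two further inferences go too far. Multiplying an assumed carry-over rate by an assumed step-down rate gives the share of subjects with such a record, not the rise in the primary variable. And a concentration in Months 1-3, or in headache, somnolence, dizziness and fatigue, is conjecture: Protocol 2.4 lists those terms as frequently reported, not as likely to be ongoing at rollover.

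**What to change.** 1. **Protocol footnote k and 8.1.** Replace the undirected trigger with *an increase in intensity, or the AE becomes serious*, in line with 10.1.1 and 10.1.5.
2. **SAP 11.2.1.** Data may already be collected (the SAP amendment was approved in February 2019 and supports the final report), so the SAP sentence matters more. Suggested text: *A record that continues an AE ongoing from N01358 or N01258 is a TEAE only if its intensity exceeds the last intensity in that study's database or it has become serious; records of reduced intensity or seriousness are listed only.* State also how a missing intensity is handled in this comparison.
3. **Matching.** Link by subject number, term and contiguous dates. Subject numbers carry over (Protocol 7.10), changes on site transfer are recorded (SAP 3.9), and footnote k already draws ongoing events from the core-study databases.

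The cost is one phrase in two protocol places, one SAP rule and a small new derivation, since no current SAP analysis matches adverse events to core-study records. TEAE counts may fall slightly. If matching finds no step-downs, the tables do not change and the report can say so.

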5.3 Visit schedule

Visits to the clinical site will be scheduled as follows:

- First year:
 - First 3 months: 1 visit every month: Minimal Evaluation Visit (MEV) alternating with the Full Evaluation Visit (FEV)
 - Next 9 months: 1 visit every 3 months: FEV alternating with MEV
- Second and subsequent years:
 - 1 visit every 3 months: MEV alternating with FEV/Yearly Evaluation Visit (YEV)
 - The YEV will be performed every 12 months

A full visit schedule is presented in the following table.

This document cannot be used to support any marketing authorization application and any extensions or variations thereof.

REDACTED COPY

Table 5–2: Visit schedule

First year follow-up		
Month	Visit	Type of visit
M0	V1	EV
M1	V2	MEV
M2	V3	FEV
M3	V4	MEV ^b
M4	-	-
M5	-	-
M6	V5	FEV
M7	-	-
M8	-	-
M9	V6	MEV ^b
M10	-	-
M11	-	-
Second year follow-up^a		
Month	Visit	Type of visit
M12	V7	YEV
M15	V8	MEV
M18	V9	FEV
M21	V10	MEV

EV=Entry Visit; FEV=Full Evaluation Visit; M=month; MEV=Minimal Evaluation Visit; V=Visit; YEV=Yearly Evaluation Visit

Note: “-“ denotes that no visit is scheduled in that month.

^a Subsequent years will follow the same visit schedule.

^b Liver function tests will be performed in addition to the assessments described in Section 8.3

